5.3.4 Cycles 2+: Day 22 (± 3 days)

In the event that there is a delay in starting the next cycle, the below procedures should be done weekly (approximately every 7 days, or more frequently if clinically indicated) and recorded as unscheduled visit:

- Vital signs (temperature, heart rate, systolic and diastolic blood pressures, and respiratory rate)
- Collect blood for evaluation of laboratory parameters ([Appendix D](#)):
 - Hematology
 - Tumor lysis labs
 - Fibrinogen level (as clinically indicated)
- Record only those medications (prescription, nonprescription, nutritional supplements) administered in conjunction with an AE
- Assess for AEs.
- Review study diary and remind patient to bring diary back at next clinic visit

5.3.5 Cycles 2+: Day 28 (± 3 days)

- Collect bone marrow (even-numbered cycles only) and peripheral blood for response assessment, PD tests ([Section 7.3](#)), and treatment guidance.
- Collect bone marrow sample to be sent to a central laboratory for MRD assessment using standardized techniques (ie, MPFC and molecular testing including NGS) (even-numbered cycles only) ([Appendix D](#))
- Additionally, patients who experience cytopenias lasting for 42 days from prior cycles or suspected of relapse or disease progression will have bone marrow collected on Day 28 [± 3 days]. If the bone marrow procedure is nonproductive or not diagnostic, it must be repeated within 7-10 days. In addition, 6 to 8 bone marrow slides will be prepared and sent to the Sponsor. Details regarding the collection and shipping of these slides are provided in the Laboratory Manual.
- Record only those medications (prescription, nonprescription, nutritional supplements) administered in conjunction with an AE
- Assess for AEs
- Review study diary and remind patient to bring diary back at next clinic visit

5.4 End of Treatment Assessments

If, at any time, a patient discontinues study treatment, a visit should be scheduled as soon as possible and within 14 days of the last dose of study drug or within 14 days of the decision to discontinue study treatment. If the decision to withdraw the patient occurs at a regularly scheduled visit, that visit may become the End of Treatment visit rather than having the patient return for an additional visit.

- Abbreviated physical examination (AE- or symptom-directed exam) including weight (kg) and other measures of disease and disease symptoms, eg, extramedullary disease
- Vital signs (temperature, heart rate, systolic and diastolic blood pressures)
- ECOG PS ([Appendix B](#))
- 12-lead ECG only if clinically indicated
- Collect blood for evaluation of laboratory studies ([Appendix D](#)):
 - Hematology
 - Full serum chemistry panel

- Fibrinogen level (only required if clinically indicated)
- Record only those medications (prescription, nonprescription, nutritional supplements) administered in conjunction with an AE
- Urinalysis
- Collect bone marrow and peripheral blood samples (if not done within the previous 30 days):
 - Collect bone marrow and peripheral blood for response assessment, PD tests ([Section 7.3](#)), and treatment guidance.
 - Collect bone marrow sample to be sent to a central laboratory for MRD assessment using standardized techniques (ie, MPFC and molecular testing including NGS) ([Appendix D](#))
 - If the bone marrow procedure is nonproductive or not diagnostic, it must be repeated within 7-10 days. In addition, 6 to 8 bone marrow slides will be prepared and sent to the Sponsor. Details regarding the collection and shipping of these slides is provided in the Laboratory Manual.
- Assess for AEs
- Collect study diary

5.5 Follow-up Assessments

Patients will be contacted by telephone to record data on PBRC and/or platelet transfusions occurring within 56 days after the last dose of study drug. Patients will also be contacted by telephone to assess for date of death, date of stem cell transplant, date of relapse, or continued remission for 2 years:

- Year 1: Phone calls monthly (± 5 days) beginning the month after the patient completes the end-of-study assessments to 12 months after End of Treatment visit regardless of how many cycles a patient receives (Year 1=Day of First Treatment plus 12 months).
- Year 2: Phone calls every other month (± 5 days) during Year 2 (Months 14 to 24 after End of Treatment visit).

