6.2 Reasons for Withdrawal from Study Treatment

A patient may be permanently removed from study treatment for any of the following reasons:

- Failure to achieve a CR, CRi, CRh, PR, or clinical benefit. Patients not demonstrating evidence of CR, CRi, CRh, PR, or clinical benefit after the first cycle of treatment will be considered for removal from the study, although with permission of the Medical Monitor, treatment may continue if clinically indicated and provided there is no evidence of \geq Grade 3 toxicity considered at least possibly related to alvocidib.
- An excessive Grade 3-4 toxicity without a response to treatment or occurrence of any other adverse event, concurrent illness or laboratory abnormality which, in the opinion of the Principal Investigator, warrants the patient's permanent withdrawal
- Patient noncompliance, defined as refusal or inability to adhere to the study schedule;
- At the request of the patient, Principal Investigator, the Sponsor, or regulatory authority;
- Patient is lost to follow-up;
- Patient becomes pregnant while on study;
- Patient begins another treatment for their disease; or
- Patient death.

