7.2 Efficacy Endpoints

Primary Endpoint

- Combined Complete Remission Rate = CR + CRi as defined by the International Working Group Criteria and 2017 European LeukemiaNet

Secondary Endpoints

- Median Overall Survival (OS) = Time from treatment (Day 1) until death from any cause
- CR_{MRD-} = Percentage of patients achieving complete response (CR) whose bone marrow is determined to be negative for MRD using standardized techniques (ie, MPFC and molecular testing including NGS)
- CR Rate = Percentage of patients achieving:
 - CR = Bone marrow blasts <5%; absence of blasts with Auer rods; absence of extramedullary disease; hematologic recovery (absolute neutrophil count [ANC] ≥1000/µL and platelet count ≥100,000/µL)

- Composite CR rate = Combined percentage of patients achieving one of the following:
 - CR
 - CRi = Meets all CR criteria but with only full recovery of one peripheral blood cell type (ie, ANC \geq 1000/ μ L **or** platelet count \geq 100,000/ μ L)
 - CRh = Meets all CR criteria but with only partial recovery of **both** peripheral blood cell types (ie, ANC \geq 500/ μ L **and** platelet count \geq 50,000/ μ L)
- Combined Response rate = Combined percentage of patients achieving one of the following:
 - CR
 - CRi
 - CRh
 - Morphologic leukemia-free state (MLFS) = Bone marrow blasts <5%; absence of blasts with Auer rods; absence of extramedullary disease; no hematologic recovery required
 - Partial Response (PR) = Meets all hematologic values required for CR but with a decrease of at least 50% in the percentage of blasts to \geq 5% to \leq 25% in bone marrow
- Event-free Survival (EFS) = Time from first treatment (Day 1) until (a) treatment failure, (b) relapse after CR/CRi/CRh, or (c) death from any cause, whichever occurs first, censored at 2 years
- Duration of Composite CR = Time from first documented response of CR, CRi, or CRh to relapse or death from any cause
- Rates of 28- and 56-day Transfusion Independence (TI) = Percentages of patients who do not receive red blood cell (RBC) transfusions, platelet (PLT) transfusions, and neither RBC nor PLT transfusions for 28 and 56 days; comprised of 6 secondary endpoints:
 - 28-day RBC TI
 - 28-day PLT TI
 - 28-day TI (both RBC and PLT)
 - 56-day RBC TI
 - 56-day PLT TI
 - 56-day TI (both RBC and PLT)

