28- and 56-day TI will be summarized in 2x2 shift tables showing the percentages of patients who are transfusion independent at baseline according to review of medical charts versus the percentages of patients who achieve transfusion independence at any time during the study.

Effort will be made to collect transfusion information for 56 days following withdrawal from the study to properly classify a patient's post-treatment TI status. Patients not already classified as transfusion independent and who cannot be followed will be classified as 'status unknown' for the required time to establish TI.

Exploratory Endpoints

- To evaluate potential biomarkers including but not limited to MCL-1 dependence, genetic mutations, and other biomarkers associated with AML.
- Additional exploratory analyses may be performed if useful in the interpretation of the data.

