APPENDIX A – SCHEDULES OF ACTIVITIES
Arm 1 (ALDAC): Schedule of Activities

TESTS/PROCEDURES	SCREENING												ALL TREATMENT CYCLES (CYCLE = 28 DAYS)													
	-14 days	-72 hours	D1	D2	D3	D4	D5	D6	D7	D8	D9	D10	D11	D12	D15	D22	D28	EOT	FU							
Visit window		±3d C2+																								
Obtain ICF	X																									
Medical history	X																									
Full PE	X																									
Abbreviated PE																										
BSA																										
Weight (kg)	X																									
Height (cm)	X																									
ECOG	X																									
Vital signs	X																									
Bone marrow & peripheral blood	X																									
Cytogenetic profiling	X																									
12-lead ECG	X																									
Pregnancy test	X																									
Hematology	X	X	X C2																							
Full chemistry panel	X	X	X C2+																							
Pre-infusion TLS labs				X																						
Post-infusion TLS labs				Only C1																						
Coagulation				X Only C1	X Only C1																					
Urinalysis				X C2+*																						
Blood transfusions																										
Lumbar puncture for CNS disease	X*																									
Review Inc/Exc Criteria		X																								
Daily oral allopurinol																										
IV hydration pre & post infusion																										
Oral phosphate binder																										

twice a week during the 10 day LDAC injections

twice a week during the 10 day LDAC injections

Recorded from 56 days prior to first study treatment dose, through 56 days after last dose of study treatment

Mandatory from 72 hours prior to D1 up to C1D28. As clinically indicated for subsequent cycles.

For C1, mandatory

X C2+***

TESTS/PROCEDURES	ALL TREATMENT CYCLES (CYCLE = 28 DAYS)																		
	-14 days	-72 hours	D1	D2	D3	D4	D5	D6	D7	D8	D9	D10	D11	D12	D15	D22	D28	EOT	FU
Visit window		±3d C2+																±3d	±5d
Assess patient's hydration level																			
Prophylactic antibiotics, antifungals per site SOC																			
Antiviral per site SOC																			
Alvocidib infusion																			
LDAC injection																			
Provide / review patient diary																			
Con meds																			
Assessment of AEs																			
Phone call to patient																			

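### Transfusion collection stops 56 days after the last dose in one set of sections and 56 days after withdrawal in another, so some late-recovering patients cannot be documented as 56-day transfusion independent

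*Protocol*

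**What the plan says.** Transfusion independence (TI) is assessed over two window lengths for red cells, platelets and both: "neither RBC nor PLT transfusions for 28 and 56 days; comprised of 6 secondary endpoints" (Protocol 7.2). The shift tables credit patients who "achieve transfusion independence at any time during the study".

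Two rules govern how long the data are gathered.

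- **Endpoint text** (synopsis objectives, Section 3, Section 7.2): "Effort will be made to collect transfusion information for 56 days following withdrawal from the study to properly classify" post-treatment TI status. Patients who are not already independent and cannot be followed go into a status-unknown category.
- **Collection instructions.** Section 5.5 and the synopsis follow-up text have telephone contacts capture "platelet transfusions occurring within 56 days after the last dose of study drug". The transfusion row of the schedules in Appendix A and SAP Section 18 reads "Recorded from 56 days prior to first study treatment dose, through 56 days after last dose of study treatment".

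No section says that the last dose and withdrawal are the same date. Section 4.4.2 puts the last dose of a cycle on Day 15 in both arms. Section 5.2.6 puts the Cycle 1 marrow assessment on Day 28 (±3 days). Section 5.4 allows the End of Treatment visit "within 14 days of the decision to discontinue study treatment". Section 6.2 lists "Patient begins another treatment for their disease" as a reason to leave study treatment, but no section ends a TI window at that point.

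**The concern.** A 56-day endpoint needs 56 observed days after the last transfusion. If observation also lasts 56 days and starts at the last dose, nothing is left for a patient whose transfusion need ends a week or two after that dose. The endpoint text appears to foresee this by extending the effort to 56 days past withdrawal, but the instructions that sites work from do not carry the extension.

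At stake is the classification of a specific group on the three 56-day endpoints: patients whose marrow recovers between the last dose and the decision to stop, and who have no qualifying window from earlier cycles. A smaller, separate matter concerns the three 28-day endpoints. Nothing prevents a window that falls entirely on the next AML treatment from being counted for this regimen.

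**Working it through.** The plan states no figure to reproduce, so this is day counting.

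**Inputs**

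- Last dose on Day 15 (4.4.2), with a ±2-day window (5.2.3).
- Response assessment on Day 28 ±3 (5.2.6).
- At most 6 weeks between cycle starts, so the next cycle starts by Day 43 (5.3).
- Collection of 56 days from either anchor, and TI windows of 28 and 56 days.
- Assumptions: one cycle; withdrawal means withdrawal from study treatment and falls on Day 28; collection covers days +1 to +56 after the anchor.

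**End of collection**

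- Last-dose anchor: 15 + 56 = Day 71.
- Withdrawal anchor: 28 + 56 = Day 84.
- Shortfall: 84 − 71 = 13 days. Days observed after withdrawal under the last-dose rule: 71 − 28 = 43.

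**Room for a window.** The number of start days for an L-day window inside days a to b is b − a − L + 2, or zero if that is negative.

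| Rule and window | Calculation | Start days |
|---|---|---|
| Last dose, 56-day, wholly after dose | 71 − 16 − 56 + 2 | 1 (Day 16) |
| Last dose, 56-day, wholly after withdrawal | 71 − 29 − 56 + 2 = −12 | 0 |
| Last dose, 56-day, any time from Day 1 | 71 − 1 − 56 + 2 | 16 (Days 1–16) |
| Last dose, 28-day, wholly after dose | 71 − 16 − 28 + 2 | 29 (Days 16–44) |
| Withdrawal, 56-day, wholly after dose | 84 − 16 − 56 + 2 | 14 (Days 16–29) |

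**Who is affected.** A patient last transfused on Day t completes L free days on Day t + L.

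- 56-day TI, last-dose rule: t ≤ 71 − 56 = Day 15.
- 56-day TI, withdrawal rule: t ≤ 84 − 56 = Day 28.
- 28-day TI, last-dose rule: t ≤ 71 − 28 = Day 43.

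The two rules therefore differ on 56-day TI for last transfusions on Days 16 to 28. A patient last transfused on Day 20 has 51 free days on Day 71 and would complete the window on Day 76. Within one cycle, no window starting on Day 1 or later can have been completed before such a transfusion.

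**Sensitivity.** Both anchors add 56 days, so the shortfall is simply withdrawal day minus last-dose day.

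| Last dose | Withdrawal Day 25 | Day 28 | Day 31 | Day 43 |
|---|---|---|---|---|
| Day 13 | 12 | 15 | 18 | 30 |
| Day 15 | 10 | 13 | 16 | 28 |
| Day 17 | 8 | 11 | 14 | 26 |

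A decision on Day 28 followed by an End of Treatment visit on Day 42, with that visit taken as withdrawal, gives 42 − 15 = 27 days. That is a late case, because Sections 5.4 and 6.1 let the decision visit serve as the End of Treatment visit.

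**Later therapy.** The latest 28-day window runs from Day 44 to Day 71. If another AML treatment starts by Day 44, that window lies wholly on it. The calls in Section 5.5 ask about death, transplant, relapse and remission, but not about the start of another drug treatment.

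**The case against.** The strongest reply is that the two texts can coexist. The endpoint text promises only effort, monthly calls continue through Year 1, and a site could record transfusions after Day 71. Patients who cannot be followed are classed as status unknown, so they need not count as failures. Patients with a response or clinical benefit may go on to further cycles, and their windows can run across those cycles. The limit bites only in the last cycle.

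Most of this is fair and limits the point, but it does not remove the mismatch. Sites follow Section 5.5 and the schedules, which name the shorter period. A patient who can be reached by telephone, but whose collection period has expired, is not obviously one who cannot be followed, so the status-unknown rule does not clearly apply.

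Three stronger readings are tempting, and the documents do not support them.

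- *The shift table compares a full baseline window with a truncated on-study one.* The reverse holds. Baseline is a 56-day look-back with room for one 56-day window, while a one-cycle patient is observed on study for 71 days with 16 possible start days.
- *Later therapy inflates 56-day TI.* Under the last-dose rule a 56-day window must start no later than the day after the last dose. Independence first gained on a subsequent therapy cannot fill it. Only the 28-day endpoints are open to this.
- *The endpoint is biased against responders in general.* Continuing responders have windows across cycles, and it is unclear whether an affected patient is not independent or of unknown status. Neither the direction nor the size of any bias is established.

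**Conclusion.** The inconsistency is real and should be reconciled. For a one-cycle patient with the last dose on Day 15 and withdrawal on Day 28, the operational rule stops 13 days short of the endpoint text, and further short if the decision to stop comes later. A patient last transfused on Days 16 to 28, with no earlier qualifying window, cannot be documented as 56-day TI under that rule. The plan does not say whether this patient is not TI or status unknown. For 28-day TI the last transfusion can be as late as Day 43, so that endpoint is much less affected by the cut-off, but it lacks a stop at the next AML therapy.

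This rests on nominal visit days and on reading withdrawal as withdrawal from study treatment. If it meant leaving the 2-year follow-up, the gap would be far larger.

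Severity is low. These are descriptive secondary endpoints, the study closed with 11 patients (7 lead-in, 4 in Stage 1), and SAP Section 11 lists no TI summary, although SAP Sections 3.1.2 and 3.2.2 keep the six endpoints.

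**What to change.** Use one anchor in the synopsis, Section 5.5, both Appendix A schedules and SAP Section 18, and have the endpoint text refer to the same date. Record transfusions through 56 days after withdrawal from study treatment, dated by the End of Treatment visit, or until another AML treatment starts, whichever is first. Ask for that start date on the follow-up calls.

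The stop at new therapy is an essential part of the change. Extending collection to Day 84 without it would allow a 56-day window on Days 29 to 84, which could fall on a subsequent treatment.

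State that a patient whose transfusion-free run is still open and too short when collection ends is status unknown, unless a qualifying window was already completed. That rule catches short runs as well as long ones, so list the run length beside the category.

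The cost is wording plus a transfusion and new-therapy question on the monthly Year 1 calls already scheduled. No visit is added. For the closed trial, it is enough to state the cut-off used and the handling of incomplete windows wherever transfusion data are listed, and to correct the text before it is reused.

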6. OFF-STUDY CRITERIA

6.1 Withdrawal of Patients from Study Treatment

All patients have the right to withdraw at any time during treatment without prejudice. Circumstances may occur under which a patient may be permanently removed from the study. The criteria used to justify withdrawal of a study patient are described below.

In the event of a premature withdrawal, the assessments for the End of Treatment visit, as detailed in the Schedule of Activities (see [Appendix A](#)), should be completed at the time of the withdrawal, wherever possible, including dates of remission and death. If the study patient is prematurely withdrawn due to an adverse event(s), attempts should also be made to clinically follow the study patient until the event is resolved, stable or permanent as determined by the Principal Investigator and Sponsor.

6.2 Reasons for Withdrawal from Study Treatment

A patient may be permanently removed from study treatment for any of the following reasons:

- Failure to achieve a CR, CRi, CRh, PR, or clinical benefit. Patients not demonstrating evidence of CR, CRi, CRh, PR, or clinical benefit after the first cycle of treatment will be considered for removal from the study, although with permission of the Medical Monitor, treatment may continue if clinically indicated and provided there is no evidence of \geq Grade 3 toxicity considered at least possibly related to alvocidib.
- An excessive Grade 3-4 toxicity without a response to treatment or occurrence of any other adverse event, concurrent illness or laboratory abnormality which, in the opinion of the Principal Investigator, warrants the patient's permanent withdrawal
- Patient noncompliance, defined as refusal or inability to adhere to the study schedule;
- At the request of the patient, Principal Investigator, the Sponsor, or regulatory authority;
- Patient is lost to follow-up;
- Patient becomes pregnant while on study;
- Patient begins another treatment for their disease; or
- Patient death.

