	
Those who achieve a CR, CRi, CRh, or MLFS (ie, <5% blasts in bone marrow) should not be given subsequent cycles until ANC >0.5 and platelets >50. If treatment is delayed >2 weeks for cytopenias, a bone marrow biopsy should be performed to reassess disease status.
 
Patients not demonstrating evidence of CR, CRi, MLFS, PR, or clinical benefit after 4 cycles of treatment will be considered for removal from the study, although with permission of the Medical Monitor, treatment may continue if clinically indicated (in the event of toxicities see the recommendations in Table 3, if applicable).

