	
Patients not demonstrating evidence of CR, CRi, CRh, MLFS, PR, or clinical benefit after the first 4 cycles of treatment will be considered for removal from the study, although with permission of the Medical Monitor, treatment may continue if clinically indicated (in the event of toxicities see the recommendations in Table 3, if applicable). Please see Section 5.3 for details.
 
End of Treatment
 
Abbreviated physical examination (AE- or symptom directed exam) including weight (kg) and other measures of disease and disease symptoms, eg, extramedullary diseaseVital signsECOG PS (Appendix B)12-lead ECG only if clinically indicatedCollect blood for evaluation of laboratory studies (Appendix D):
HematologyFull serum chemistry panelFibrinogen level (only required if clinically indicated)Record only those medications (prescription, nonprescription, nutritional supplements) administered in conjunction with an AEUrinalysisCollect bone marrow and peripheral blood (if not done within the previous 30 days):
Collect bone marrow and peripheral blood for response assessment, PD tests, and treatment guidance.Collect bone marrow sample to be sent to a central laboratory for MRD assessment using standardized techniques (ie, MPFC and molecular testing including NGS).If the bone marrow procedure is nonproductive or not diagnostic, it must be repeated within 7-10 days. In addition, 6 to 8 bone marrow slides will be prepared and sent to the Sponsor. Details regarding the collection and shipping of these slides is provided in the Laboratory Manual.Assess for AEsCollect study diary 
Follow Up
 
Patients will be contacted by telephone to record data on PBRC and/or platelet transfusions occurring within 56 days after the last dose of study drug. Patients will also be contacted by telephone to assess for date of death, date of stem cell transplant, date of relapse, or continued remission for 2 years.

--	--

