Those who achieve a CR, CRi, CRh, or MLFS (i.e. <5% blasts in bone marrow) **should** not be given **subsequent cycles** until ANC >0.5 and platelets >50. If treatment is delayed >2 weeks for cytopenias, a bone marrow biopsy should be performed to reassess disease status.

Patients not demonstrating evidence of CR, CRi, MLFS, PR, or clinical benefit after 4 cycles of treatment will be considered for removal from the study, although with permission of the Medical Monitor, treatment may continue if clinically indicated (in the event of toxicities see the recommendations in **Table 3**, if applicable).

[figure not shown]

Figure 1: Treatment Schema for Lead-in Cohort and Stage 1

ALDAC=alvocidib plus low-dose cytarabine; LDAC=low-dose cytarabine

* If patients treated in the lead-in cohort are still on study when Amendment 2 is approved and the DSMB has confirmed safety, they may be permitted to shift to the higher alvocidib dose regimen, ie, ALV 50 mg/m² IV bolus, per investigator discretion.

**Alvocidib dose will be 50 mg/m² beginning in Cycles 2+ after completion of the safety lead-in cohort. No dose reductions will be permitted after the lead-in cohort is completed.

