4.5 Management of Toxicities and Dosage Modifications

Table 3 provides the recommended dose modifications for toxicities (graded using NCI CTCAE version 5.0) in AML.

Table 3: Recommended Dose Modifications

Event	Occurrence	Action
Hematologic Toxicities		
Grade 4 neutropenia with or without fever or infection; or Grade 4 thrombocytopenia	Occurrence prior to achieving remission	Transfuse blood products, administer prophylactic and treatment anti-infectives as clinically indicated. In most instances, study treatment should not be interrupted due to cytopenias prior to achieving remission.
	Occurrence after achieving remission and lasting at least 7 days	Delay subsequent study treatment cycle and monitor blood counts. Administer granulocyte colony-stimulating factor (G-CSF) if clinically indicated for neutropenia following consultation with the Medical Monitor. Once the toxicity has resolved to a clinically acceptable situation, resume study treatment at the same dose and schedule (no dose reductions permitted after completion of lead-in cohort.)

Suggested doses of supportive care therapies are provided; however, adjustment of the dosages based on the patient's clinical condition or each institution's standard of care is permitted.

Patients will be provided with a diary to track diarrheal episodes and doses of required concomitant medications (ie, antibiotics, antivirals, antifungals, allopurinol, phosphate binders, etc). The diary should be brought to every clinic visit so study staff can monitor compliance.

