5.3 Cycles 2+

Patients who achieve CR, CRi, CRh, MLFS, PR, or clinical benefit after the first cycle (completion of all doses) may receive additional optional cycles of treatment until disease progression (in the event of toxicities see the recommendations in [Table 3](#), if applicable).

Those who achieve a CR, CRi, CRh, or MLFS (ie, <5% blasts in bone marrow) should not be given **subsequent cycles** until ANC >0.5 and platelets >50. If treatment is delayed >2 weeks for cytopenias, a bone marrow biopsy should be performed to reassess disease status.

Patients not demonstrating evidence of CR, CRi, CRh, MLFS, PR, or clinical benefit after 4 cycles of treatment will be considered for removal from the study, although with permission of the Medical Monitor, treatment may continue if clinically indicated (in the event of toxicities see the recommendations in [Table 3](#), if applicable).

There is a maximum limit of 6 weeks between the start of cycles unless otherwise discussed with the medical monitor.

5.3.1 Cycles 2+: At Least 2 Hours Prior to First Dose (± 3 days)

During Cycles 2+, pretreatment IV hydration, oral allopurinol, and oral phosphate binder may be discontinued if serum uric acid and phosphorus levels are within normal limits and there is no evidence of TLS.

Should TLS be suspected during subsequent cycles, perform the following procedures at least 2 hours prior to starting therapy on Day 1 (unless otherwise stated):

- Initiate supportive care measures prior to first dose in all patients to minimize the likelihood of TLS:
 - Administer pretreatment IV hydration and determine if oral allopurinol and oral phosphate binder are still clinically indicated (see [Section 4.5.1](#))

- Assess patient for adequate hydration at all study visits and replace excessive fluid losses, including from diarrhea, unless otherwise clinically indicated ([Section 4.5.1.2](#) and [Section 4.5.1.3](#))
- Review study diary and remind patient to bring diary back at next clinic visit

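### Section 6.2 reviews non-responders for removal after Cycle 1, with a Grade 3 toxicity condition on continuing; the synopsis and Sections 4.4.2 and 5.3 set that review after 4 cycles without the condition

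*Protocol*

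**What the plan says.** Protocol Section 6.2 lists the reasons for taking a patient off study treatment. The first is lack of response: patients without CR, CRi, CRh, PR or clinical benefit "after the first cycle of treatment will be considered for removal from the study". They may go on with the Medical Monitor's permission, but only if there is no evidence of toxicity at or above the level given as "Grade 3 toxicity considered at least possibly related to alvocidib".

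Three other parts of the Protocol describe the same step at a different time:

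- Section 5.3: patients without "CR, CRi, CRh, MLFS, PR, or clinical benefit after 4 cycles of treatment will be considered for removal".
- Section 4.4.2: "Patients not demonstrating evidence of CR, CRi, MLFS, PR, or clinical benefit after 4 cycles of treatment will be considered for removal". The synopsis uses the same list and time point under additional cycles of treatment.
- The synopsis entry for Cycles 2+: "after the first 4 cycles of treatment will be considered for removal from the study".

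All of these also allow continuation with the Medical Monitor's permission. On toxicity they give only a pointer: "in the event of toxicities see the recommendations in Table 3, if applicable". As read from the PDF, Table 3 in Section 4.5 has one type of entry, "Grade 4 neutropenia with or without fever or infection; or Grade 4 thrombocytopenia".

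The synopsis and Sections 4.4.2 and 5.3 also contain a permissive sentence: patients with a listed response or clinical benefit after Cycle 1 may receive further optional cycles.

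**The concern.** The sentences share their structure and their Medical Monitor exception, so they read as one decision step given two time points and two sets of conditions. All of them are current operative text. A site working from Section 6.2 would review a non-responder after Cycle 1. A site working from Section 4.4.2 or 5.3 would find the review set after Cycle 4.

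The toxicity condition differs as well. Take a patient with neither response nor clinical benefit after Cycle 1 who has had a related Grade 3 non-hematologic event. Section 6.2 closes the continuation route for that patient; the 4-cycle text states no such bar.

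The statistical interest lies in how response is ascertained. Section 11.4.2 counts patients whose best response is CR or CRi and states no fixed assessment window. How long a non-responder stays on treatment therefore helps determine how many scheduled marrows can show a response.

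**Working it through.** **The passages side by side**

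| Place in Protocol | Review after | Responses listed, besides clinical benefit | Toxicity wording |
|---|---|---|---|
| Synopsis, additional cycles | 4 cycles | CR, CRi, MLFS, PR | Pointer to Table 3 |
| Synopsis, Cycles 2+ | 4 cycles | CR, CRi, CRh, MLFS, PR | Pointer to Table 3 |
| Section 4.4.2 | 4 cycles | CR, CRi, MLFS, PR | Pointer to Table 3 |
| Section 5.3 | 4 cycles | CR, CRi, CRh, MLFS, PR | Pointer to Table 3 |
| Section 6.2 | 1 cycle | CR, CRi, CRh, PR | No related toxicity of Grade 3 or higher |

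**Toxicity.** Table 3 covers Grade 4 cytopenias, so the pointer to it does not restate the Section 6.2 condition. Toxicity is addressed elsewhere. The second bullet of Section 6.2 makes excessive Grade 3-4 toxicity in a patient who has not responded a separate reason for removal, with no cycle limit. Sections 4.5.1 and 4.5.2 allow related moderate-to-severe events to end treatment. None of these repeats the condition on continuing.

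**Response lists.** MLFS is in every list except that of Section 6.2. Read literally, a patient with MLFS after Cycle 1 is a candidate for removal under 6.2 unless counted as having clinical benefit, a term the Protocol does not define. Under Sections 4.4.2 and 5.3 the same patient may receive further cycles. The missing CRh is editorial. By the Section 7.2 definitions a CRh patient meets all CR criteria apart from full count recovery, and MLFS requires no count recovery. Every CRh patient therefore meets the MLFS definition and is already covered where MLFS is listed. Section 4.4.2 itself names CRh in its sentence on count recovery ("Those who achieve a CR, CRi, CRh, or MLFS").

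**Scheduled response marrows.** Sections 5.2.6 and 5.3.5 and Appendix A schedule marrow at Day 28 of Cycle 1 and then of even-numbered cycles, each with a window of 3 days either way. Cycles last 28 days. With Cycle 1 Day 1 as study day 1 and no delay, Day 28 of cycle c falls on study day 28 × (c − 1) + 28:

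- Cycle 1: 28 × 0 + 28 = 28
- Cycle 2: 28 × 1 + 28 = 56
- Cycle 4: 28 × 3 + 28 = 112

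Read as 1 cycle, a non-responder has one scheduled marrow (Cycle 1). Read as 4 cycles, there can be three (Cycles 1, 2 and 4), a difference of 3 − 1 = 2. The last look comes 112 − 28 = 84 days later.

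The 84 days is a nominal figure, not a ceiling. Section 5.3 allows up to 6 weeks between cycle starts, or longer after discussion with the Medical Monitor. With 42-day spacing, Cycle 4 Day 28 is study day 42 × 3 + 28 = 154, which is 154 − 28 = 126 days after the Cycle 1 look.

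The End of Treatment marrow (Section 5.4) is skipped if one was taken in the previous 30 days, so it would not normally add a look soon after Day 28. Section 5.3.5 allows extra marrows for prolonged cytopenia or suspected relapse or progression.

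**The case against.** The strongest reply is that little turns on this. Every version says only that removal will be considered, Section 6.2 opens by saying a patient may be removed, and the Medical Monitor can permit continuation in all of them. That is right, and it means neither text is a hard stop. The point at which the question must be asked still differs, as does the condition attached to the answer.

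A second reply is that the contrast of one marrow with three is not a fixed default. The permissive Cycle 1 sentence covers only patients with a response or clinical benefit, so the 4-cycle text does not say how a patient with neither gets to Cycle 4. This stands: three marrows is one reading, and it applies only to patients with neither response nor benefit. The same gap is part of what needs reconciling.

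A third reply is that the two texts describe successive reviews, one after Cycle 1 and another after Cycle 4. No section says so or refers to another review, and the 4-cycle text mentions no earlier permission.

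A reader might also infer that the 4-cycle text leaves toxicity in non-responders unmanaged. The documents do not support that, given the second bullet of Section 6.2 and Sections 4.5.1 and 4.5.2. What is missing is the specific condition on continuing.

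**Conclusion.** The contradiction is real: 1 cycle in one place against 4 cycles in four passages, with the Grade 3 condition in the first only and MLFS missing from that list only. Nothing in the Protocol says which text prevails. The SAP claims precedence over the Protocol's statistical considerations, which does not settle a treatment rule.

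Its size is one scheduled response marrow against as many as three, with the last look nominally 84 days later, assuming undelayed 28-day cycles and a patient who continues under the 4-cycle reading.

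A reader might infer that this biases the CR/CRi rate or weakens the power calculation. The documents do not support that. They give no timing of response to these regimens, so neither the size nor the direction of an effect can be worked out. Nor do they show that any site or patient was handled differently because of it. The study closed with 11 patients enrolled, 4 of them in Stage 1 and none in Stage 2, and the SAP rules out inferential efficacy analysis. The point therefore concerns the plan as written. It keeps some value for reading the tables the SAP still produces on reasons for discontinuation, cycles completed and best response.

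**What to change.** Reconcile Section 6.2, Section 4.4.2, Section 5.3 and both synopsis entries so that four things agree everywhere:

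- the time point of the review;
- the list of qualifying responses, with MLFS treated the same way throughout and CRh added or left out consistently;
- the toxicity condition on continuing;
- the Cycle 1 continuation sentence, including what happens to a patient with neither response nor clinical benefit after that cycle.

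Which rule applies is for the sponsor's clinicians to decide; this review takes no position on it. The cost is wording in those places. No visits or procedures need to be added, and the primary endpoint definition is unchanged. Since the study is closed, a sentence in the clinical study report stating which rule was in force would serve readers of the final tables.
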